### **3.3 Exclusion Criteria**

Subject will be excluded from participation if any of the following apply:

At screening:

1. Subject has received investigational drug within 30 days or 5 half-lives, whichever is longer, prior to screening.
2. Subject has use of RRT within 30 days prior to screening.
3. Subject has CKD stage 4 or 5, or stage 3 (i.e., eGFR 30-59 mL/min per 1.73m^2) with a known history of eGFR < 30 mL/min per 1.73 m^2 as per CKD-EPI or MDRD equation within 6 months prior to screening.
4. Subject has a prior kidney transplantation.
5. Subject has a known or suspected glomerulonephritis (other than Diabetic Kidney Disease).
6. Subject has confirmed or treated endocarditis, or other current active infection requiring antibiotic treatment, within 30 days prior to screening.
7. Subject is using prohibited medications as specified in the concomitant medication section of the protocol [Section 5.1.3.1 Prohibited and Restricted Treatment].
8. Subject has a prior history of intravenous drug abuse within 1 year prior to screening.
9. Subject has a known chronic liver disorder with Child-Pugh B or C classification.
10. Subject has any of the following abnormal liver or kidney function parameters as assessed at screening. (If the results from the central laboratory are not yet available at time of randomization, results from local laboratory within 7 days before the surgery can be used for verifying this criterion. The subject will not be excluded from the study if central laboratory results from screening are exclusionary and are available only after randomization.):
  - Alanine aminotransferase (ALT), aspartate aminotransferase (AST) to > 2 times the upper limit of normal (ULN) or bilirubin increased to > 1.5 times the ULN (not due to previously diagnosed Gilbert's syndrome).
  - eGFR < 30 mL/min per 1.73 m^2 as per CKD-EPI equation.
11. Subject has use of left ventricular assist device (LVAD), intra-aortic balloon pump (IABP) or other cardiac devices, or catecholamines within 7 days prior to screening.
12. Subject has surgery scheduled to be performed without CPB (i.e., "Off-Pump" surgery).
13. Subject has surgery scheduled to be performed under conditions of circulatory arrest, including planned deep hypothermic circulatory arrest.
14. Subject has surgery scheduled for aortic dissection.
15. Subject has surgery for a condition that is immediately life-threatening as per the discretion of the investigator.
16. Subject has surgery scheduled to correct major congenital heart defect.

17. Subject has current or previous malignant disease. Subjects with a history of cancer are considered eligible if the subject has undergone therapy and the subject has been considered disease free or progression free for at least 5 years. Subject with completely excised basal cell carcinoma or squamous cell carcinoma of the skin and completely excised cervical cancer in situ are also considered eligible.

*Preoperatively at the Day of Surgery:*

18. Exclusion criteria 1 to 17 are applicable at this time.
19. Subject has AKI (any stage) present at presurgery baseline at the discretion of the investigator.
20. Subject has known or suspected infection/sepsis at time of presurgery baseline at the discretion of investigator.

*Perioperative Exclusion Criteria:*

21. Subject requires Extracorporeal Membrane Oxygenation (ECMO) during or after completion of surgery.
22. Subject requires ventricular assist device (VAD) during or after completion of surgery.
23. Subject has surgery performed “Off-Pump” at any time during surgery.

*General:*

24. Subject has other condition, which, in the investigator’s opinion, makes the subject unsuitable for study participation.
25. Female subject who is pregnant or lactating or has a positive pregnancy test within 72 hours prior to screening and/or randomization, has been pregnant within 6 months before screening assessment or breastfeeding within 3 months before screening or who is planning to become pregnant within the total study period.
26. Subject has a known or suspected hypersensitivity to ASP1128 or any components of the formulation used.
27. Subject is an employee of the Astellas Group or the contract research organization (CRO) involved in the study.

Waivers to the inclusion and exclusion criteria will **NOT** be allowed.

## **4 TREATMENT(S)**

### **4.1 Identification of Investigational Product(s)**

#### **4.1.1 Study Drug(s)**

ASP1128 is a sterile, clear colorless liquid supplied in a single-use vial with a coated rubber stopper and an aluminum cap.

Each vial will contain 10.5 mL formulated solution, including an overfill sufficient to deliver 10 mL of the formulated solution (containing 50 mg ASP1128).

The preparation and administration of ASP1128 will be described in the pharmacy manual. The storage conditions will be described on the product label.

#### **4.1.2 Comparative Drug(s)**

Placebo to match (PTM) is a sterile, clear colorless liquid supplied in a single-use vial with a coated rubber stopper and an aluminum cap.

The preparation and administration of PTM will be described in the pharmacy manual. The storage conditions will be described on the product label.

### **4.2 Packaging and Labeling**

All study drugs used in this study will be prepared, packaged and labeled under the responsibility of qualified staff at sponsor's designee in accordance with sponsor's designee Standard Operating Procedures (SOPs), Good Manufacturing Practice (GMP) guidelines, ICH Good Clinical Practices (GCP) guidelines and applicable local laws/regulations.

Each vial will bear a label conforming to regulatory guidelines, GMP and local laws and regulations that identifies the contents as investigational drug.

### **4.3 Study Drug Handling**

Current ICH GCP Guidelines require the investigator to ensure that study drug deliveries from the sponsor are received by the investigator/or designee and that:

- Such deliveries are recorded
- Study drug is handled and stored according to labeled storage conditions
- Study drug with appropriate expiry/retest date is used and is only dispensed to study subjects in accordance with the protocol
- Any unused study drug is returned to the sponsor

Study drug inventory and accountability records will be kept by the investigator or designee. Study drug accountability throughout the study must be documented and reconciled. The following guidelines are therefore pertinent:

- The investigator or designee agrees not to supply study drugs to any persons except the eligible subjects in this study in accordance with the protocol.
- The investigator or designee (i.e., study drug manager) will keep the study drugs in a pharmacy or other locked and secure storage facility under controlled storage conditions, accessible only to those authorized by the investigator to dispense these study drugs.
- A study drug inventory will be maintained by the investigator or designee (i.e., study drug manager). The inventory will include details of material received and a clear record of when they were dispensed and to which subject.
- At the conclusion or termination of this study, the investigator or designee (i.e., study drug manager) agrees to conduct a final drug supply inventory and to record the results of this inventory on the Drug Accountability Record. It must be possible to reconcile delivery records with those of used and/or returned study drug. Any discrepancies must

be accounted for and documented. Appropriate forms of deliveries and returns must be signed by the site staff delegated this responsibility.

- The site staff must return study drug to the sponsor or designee at the end of the study or upon expiration unless otherwise approved by the sponsor.

## **4.4 Blinding**

### **4.4.1 Blinding Method**

For the purpose of this study, the efficacy and safety of ASP1128 and placebo will be compared in a double-blind manner. ASP1128 and placebo will be indistinguishable in appearance. Packaging for each treatment group will also be indistinguishable in appearance. The randomization number will be assigned based on information obtained from the interactive response technology (IRT). The randomization code will remain confidential until completion of the study.

### **4.4.2 Confirmation of the Indistinguishability of the Study Drugs**

The appearance and the form of both the drug and packaging of ASP1128 are identical to those of their matching placebo.

### **4.4.3 Retention of the Assignment Schedule and Procedures for Treatment Code Breaking**

The randomization list and study drug blind will be maintained by the IRT system.

### **4.4.4 Breaking the Treatment Code for Emergency**

The treatment code for each randomized subject will be provided by the IRT in the event of a medical emergency requiring knowledge of the treatment assigned to the subject. The IRT will be programmed with blind-breaking instructions that may only be requested by the investigator or subinvestigators designated to have access to perform blind-break. In case of a medical emergency, the investigator has the sole responsibility for determining if unblinding of subject's treatment assignment is warranted. Subject safety must always be the first consideration in making such determination. If the investigator decides that unblinding is warranted, the investigator should make every effort to contact the sponsor prior to unblinding a subject's treatment assignment unless this could delay emergency treatment for the subject.

The investigator must have confirmed functionality to access code-break through the IRT system and must have a designated back up (e.g., redundant processes) to support emergency unblinding requirements.

Prior to randomization, subjects should be provided with information that includes the site emergency contact number and back-up contact number in case of a medical emergency. Any unblinding by the investigational staff must be reported immediately to the sponsor and include an explanation of why the study drug was unblinded. If unblinding is associated with a SAE the investigator is to follow the instructions in [Section 5.5.5 Reporting of Serious Adverse Events].

Care should be taken to limit knowledge of the randomization arm, in case this could affect the blinding of other subjects or future study assessment for the subject.

#### **4.4.5 Breaking the Treatment Code by the Sponsor**

The sponsor may break the treatment code for subjects who experience a Suspected Unexpected Serious Adverse Reaction (SUSAR), in order to determine if the individual case or a group of cases requires expedited regulatory reporting. Individual Emergency Codes will be provided to the limited staff who are responsible to break the codes for all SUSAR cases for reporting purposes.

### **4.5 Assignment and Allocation**

Subjects who have a NC AKIRisk score of  $> 0.3 \text{ (ng/ml)}^2/1000$  will be randomized in a 1:1 ratio to a treatment arm according to the randomization schedules through IRT. There will be a cap on the proportion of subjects randomized with a eGFR  $< 45 \text{ mL/min per } 1.73 \text{ m}^2$  (assessed at visit 1 as per CKD-EPI equation) of 20% of total randomized. Randomization will also be stratified for eGFR  $< 45$  and  $\geq 45 \text{ mL/min per } 1.73 \text{ m}^2$  to allocate subjects equally between study groups within each stratification. The site personal will dispense the treatment according to the IRT system's assignment. Specific procedures for randomization through the IRT are contained in the study procedures manual.

Subjects with NC AKIRisk score of  $0.3 \text{ (ng/mL)}^2/1000$  or less will be enrolled in the observational cohort. The observational cohort will enroll a maximum of 440 subjects.

## **5 TREATMENTS AND EVALUATION**

### **5.1 Dosing and Administration of Study Drug(s) and Other Medication(s)**

#### **5.1.1 Dose/Dose Regimen and Administration Period**

##### **5.1.1.1 Randomized Subjects**

Randomized subjects will receive 3 subsequent treatments with 100 mg of ASP1128 or matching placebo. The study drugs will be supplied as solution in 20 mL vial, which contains 10 mL of 5 mg/mL ASP1128 or 10 mL of matching placebo. The study drugs will be applied intravenously through a peripheral/central catheter. The catheter should remain until the last administration ends. The first administration of study drug will occur after randomization, as soon as possible after positive NC. If the first dose of IP administration is completed within 8 hours after T0, the second dose of IP will be administered at 24 hours after T0 and the third dose of IP will be administered at 48 hours after T0. If the first dose of IP administration is completed past 8 hours after T0, the second dose of IP will be administered at 16 hours after the start of the first dose, and the third dose of IP will be administered at 40 hours after the start of the first dose of IP. For the second and third dosing of IP, a 2-hour treatment window before or after the designated administration time is allowed.

The preparation and administration procedures of study drug will be described in the pharmacy manual.

### **5.1.1.2 Subjects in the Observational Cohort**

If the NC is negative, i.e., the AKIRisk score is  $\leq 0.3$  (ng/mL)/1000 at all assessments between 2 and 22 hours after T0, the subject cannot be randomized. These subjects will be included in the observational cohort and receive no study drug administration.

### **5.1.2 Increase or Reduction in Dose of the Study Drug(s)**

Dose increases and decreases are not allowed.

### **5.1.3 Previous and Concomitant Treatment (Medication and Non-Medication Therapy)**

The investigator should record the use of previous (up to 28 days before screening) and concomitant (any medication between screening and surgery, and following surgery to EoS) treatment in the eCRF, both medication and non-medication treatments. Subjects should be instructed not to start any new medication, both prescribed and over-the-counter (including herbals, alternative and homeopathic medicines) or non-medication treatments, without consulting the investigator, unless the new treatment is required for emergency use. In addition, non-medication treatments, including pacemakers, use of LVAD, IABP or other cardiac devices should be reported (also refer to exclusion criterion #11).

#### **Medication Treatment**

Prescribed, over-the-counter and all alternative medicines will be recorded. This includes medicines used on a chronic or as needed basis. Previous medicines taken within the 28 days prior to screening (visit 1) will be recorded.

To assess the possible contribution of nephrotoxic drugs to the occurrence of postsurgery AKI all medications taken from screening to day of surgery should be recorded. Special attention should be given to known nephrotoxins (e.g., intravenous radio-contrast) and aminoglycosides. Nephrotoxic drugs should be avoided if possible, but will not be prohibited if clinically indicated. Subjects can only be enrolled providing the subject meets the criteria for enrollment, most specifically the subject should not have AKI (any stage) present at presurgery baseline (exclusion criterion #18). If the required clinical use of nephrotoxic medications results in conditions that exclude the subject from study enrollment the subject is not eligible for study participation.

#### **Non-Medication Treatment**

During the study non-medication treatment is not prohibited if clinically indicated. Non-medication treatments, including pacemakers, use of LVAD, IABP or other cardiac devices should be reported (also refer to exclusion criterion #11). Previous treatment taken within the 28 days prior to screening (visit 1) will be recorded.

#### **5.1.3.1 Prohibited and Restricted Treatment**

A list of prohibited medications is provided in [Appendix 12.4 List of Excluded Concomitant Medications].

## **Prohibited Medications**

Medications that may significantly affect plasma creatinine levels without influencing kidney function are prohibited. These medications should be stopped more than 28 days before screening until EoS. They include cimetidine, trimethoprim, pyrimidine analogues or derivatives, phenacetin and calcitriol or alfacalcidol [Andreev, 1999].

Following surgery up to 72 hours postsurgery the use of nonsteroidal anti-inflammatory drugs [NSAIDs], angiotensin-converting enzyme [ACE] inhibitors and angiotensin receptor blockers is prohibited because of their potentially confounding effect on kidney function.

After the subject is enrolled in the observational cohort, these medications are not prohibited if clinically indicated.

## **Restricted Medications**

Restricted medication are medications, which are permitted to be used during the study provided that the subject has been taking the medication on a long-term basis, the subject remains on the medication at the same dose during the course of the double-blind treatment period and the follow-up period. Medication use is not restricted in the current study if clinically indicated. All medication used will be recorded in the eCRF.

### **Prohibited non-medication treatment (from screening until EoS)**

During the study non-medication treatment is not prohibited if clinically indicated.

#### **5.1.4 Treatment Compliance**

The dose (prepared and actual) and schedule of the study drugs administered to each subject will be recorded on the appropriate form throughout the treatment period. Reasons for dose delay, reduction or omission will also be recorded.

#### **5.1.5 Restrictions During the Study**

Subjects ensure that the investigator will be informed about following events occurring outside the study sites:

- Number of hospitalizations and number of days hospitalized
- Start of RRT
- Death

## **5.2 Demographics and Baseline Characteristics**

Baseline assessments are performed before surgery on the day of surgery, including safety laboratory tests, SCr and serum cystatin-C, biomarkers and vital signs, and will be used as baseline of each endpoint.

During surgery the following parameters will be recorded:

- Procedures (CABG surgery and/or valve surgery, thoracic aortic surgery, ECMO, use of VAD, redo thoracic surgery and indication of redo surgery).
- Duration of CPB (including aortic cross clamp time)

- Lowest intraoperative mean arterial pressure (MAP) (from the time of T0 until the time of leaving the operating room [i.e., entering the ICU])
- Perioperative fluid balance (fluid intake, UO, blood products, drain output and blood loss)
- Medication (including inotropics/vasopressors, furosemide)
- Time of incision and closing of skin
- T0 (i.e., end of CPB)
- Perioperative complications

End of surgery for this study protocol is referred to as Time point 0 (T0) which is defined as the time point when the subject comes off the CPB, i.e., the final separation from CPB and normal circulation is restored. This time point is recorded by the perfusionist in the subject chart.

### **5.2.1 Demographics**

Demographic information will be collected for all subjects at screening (visit 1) as allowed per local regulation and will include age, sex, race, ethnicity, history of smoking and history of alcohol and recreational drug use. Ejection fraction value will be collected from the most recent local echocardiography, which was conducted within 90 days before the surgery.

### **5.2.2 Medical History**

Medical history will include all significant medical conditions that have resolved prior to informed consent or are ongoing at the time of consent. Conditions that are ongoing at the time of consent will be collected as baseline conditions. Out of conditions that have resolved prior to informed consent, those can be a risk factor of AKI will be collected. Risk factors as per the KDIGO guideline [KDIGO, 2012] and the data source are described in [Table 4](#).

Several AKI risk factors will not be present at the start of the current study because they are exclusion criteria (e.g., sepsis, critical illness, cancer, major non-cardiac surgery), or will not be a significant factor because the study includes non-emergent surgery only (burns, trauma).

Details that will be collected include the onset date and recovery date for resolved conditions (including any prior AKI) and, if applicable for ongoing conditions.

**Table 4 Causes of AKI: Exposures and Susceptibilities for Non-specific AKI [KDIGO, 2012] and Additional Risk Factors Identified. Data Source for Capture at Screening or Visit 2**

| Factors  | Data Source                                   |
|--|---|
| Exposures                               |   |
| • Circulatory shock                            | Recorded perioperatively (lowest periop. MAP) |
| • Cardiovascular surgery (especially with CPB) | Inclusion criterion                           |
| • Nephrotoxic drugs                            | Recorded in previous medication               |
| • Radiocontrast agents                         | Recorded in previous medication               |
| Susceptibilities                        |   |
| • Poisonous plants and animals                 | Recorded in previous medication if applicable |
| • Dehydration or volume depletion              | Recorded perioperatively (fluid balance)      |
| • Advanced age                                 | Recorded in demographics                      |
| • Female gender                                | Recorded in demographics                      |
| • Black race                                   | Recorded in demographics                      |
| • CKD  | Assessed at screening                         |
| • Chronic diseases (heart, lung, liver)        | Recorded in medical history                   |
| • Diabetes mellitus                            | Recorded in medical history                   |
| • Anemia                                       | Assessed at screening                         |
| Additional Risk Factors                 |   |
| • Prior AKI                                    | Recorded in medical history                   |

AKI: acute kidney injury; CKD, chronic kidney disease; CPB, cardiopulmonary bypass; MAP, mean arterial pressure; periop: perioperative.

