**Table 5 Prognostic Factor Analysis Arm**

Treatment Group Code (ARMCD)	Prognostic Factor Analysis Arm (Labels in TLFs)	
P	NC positive	
O	NC negative	Total (PFAS)

ARMCD: Planned Arm Code; TLFs: Tables, Listings and Figures; NC: NephroCheck; PFAS: Prognostic Factor Analysis Set

- Duration of CPB

Duration of CPB in hours is defined as: ‘Time of T0’ - ‘Time of Onset CPB’.

- Duration of Aortic Cross-Clamp

Duration of Aortic Cross-Clamp in hours is defined as: ‘End Time of Aortic Cross-Clamp’ - ‘Start Time of Aortic Cross-Clamp’.

- Duration from Incision to Closing of Skin

Duration from Incision to Closing of Skin in hours is defined as: ‘Time of Closing of Skin’ - ‘Time of Incision of Skin’.

- Duration of Study

Duration of Study in days is defined as: ‘Date of the last date of completed or discontinued recorded in eCRF period status forms’ - ‘Date of Surgery’ + 1.

- Previous and Concomitant Treatment (Medication and Non-Medication Therapy)

Previous medication is defined as medication with at least one dose taken before the date of the screening.

Concomitant medication is defined as medication with at least one dose taken between the screening (inclusive) and surgery, and following surgery to EoS.

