**Table 6 Demographic and Baseline Characteristics**

Item	Classification
Sex	1: Male 2: Female
Age (years) [Informed Consent]	Measurement value 1: < 65 2: >= 65
	1: < 70 2: >= 70
Ethnicity	1: Not Hispanic or Latino 2: Hispanic or Latino
Race	1: White 2: Black or African American 3: Asian 4: American Indian or Alaska Native 5: Native Hawaiian or Other Pacific Islander 6: Other
Height (cm) [Screening]	Measurement value
Weight (kg) [Screening]	Measurement value 1: < 60 2: >= 60
Tobacco History	0: Never 1: Current 2: Former
Alcohol History	0: Never 1: Current 2: Former
Drug Abuse	0: Never 1: Current 2: Former
Left Ventricular Ejection Fraction (%)	Measurement value 1: < 40 2: >= 40
AKIRisk Score ((ng/mL)  /1000) [Postsurgery] 	Measurement value 1: <= 0.3 2: > 0.3 to <= 0.7 3: > 0.7
eGFR for Randomization (mL/min/1.73 m  )	Measurement value 1: < 45 2: >= 45 1: < 60 2: >= 60
Peripheral Arterial Disease 	0: No 1: Yes
Use of Intravenous Radio-contrast 	0: No 1: Yes
Protocol Version Number at Enrollment	1: Before Version 2.0 2: Version 2.0 or Later

AKI: acute kidney injury; eGFR: estimated glomerular filtration rate

1: If AKIRisk Score at post surgery is recorded several times in eCRF, the last score will be used.

2: The record of “Are there any peripheral arterial diseases?” in Demographics eCRF will be used.

3: If subjects have at least one record in the Concomitant Medication eCRF with the flag selected “YES” for of use of Intravenous Radio-contrast between the date of screening and T0 of the date of surgery, then “Yes”; otherwise “No”.

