**Table 13 Potential Risk Factors for Development of AKI and MAKE**

Risk Factor	Classification
Circulatory Shock	0: No 1: Yes
Nephrotoxic Drugs	0: No 1: Yes
Radiocontrast Agents	0: No 1: Yes
Poisonous Plants and Animals	0: No 1: Yes
Dehydration or Volume Depletion	0: No 1: Yes
Advanced Age ( $\geq 70$ years)	0: No 1: Yes
Female Gender	0: No 1: Yes
Black Race	0: No 1: Yes
CKD	0: No 1: Yes
Chronic Diseases (Heart, Lung, Liver)	0: No 1: Yes
Diabetes Mellitus	0: No 1: Yes
Anemia	0: No 1: Yes
Prior AKI	0: No 1: Yes
Left Ventricular Ejection Fraction ( $<40\%$ )	0: No 1: Yes
AKIRisk Score ( $>0.3 \text{ (ng/mL)}^2/1000$ ) [Postsurgery]	0: No 1: Yes
AKIRisk Score ( $>0.7 \text{ (ng/mL)}^2/1000$ ) [Postsurgery]	0: No 1: Yes
Peripheral Arterial Disease	0: No 1: Yes
Use of Intravenous Radio-contrast	0: No 1: Yes
Higher Risk Surgery	0: No 1: Yes
Duration of CPB ( $\geq \text{Median}$ )	0: No 1: Yes
Duration of Aortic Cross-Clamp 1 ( $\geq 0.5$ hours)	0: No 1: Yes
Duration of Aortic Cross-Clamp 2 ( $\geq 1.0$ hours)	0: No 1: Yes
eGFR Based on Serum Creatinine ( $<45 \text{ mL/min/1.73 m}^2$ ) [Baseline]	0: No 1: Yes

CKD: chronic kidney disease; AKI: acute kidney injury; CPB: cardiopulmonary bypass pump; eGFR: estimated glomerular filtration rate

In addition to the above, the following analyses will be conducted for Observational Cohort.

- Primary efficacy endpoint and secondary efficacy endpoints will be summarized for the subjects with NC positive within T0 + 24 hours and NC negative within T0 + 24 hours and all subjects in Observational Cohort. In the table, each stage of AKI-SCr72h and AKI-SCr7d and each individual outcomes of MAKE30/90 will also be summarized.
- For Observational Cohort, the association between MAKE30/MAKE90 (and also each individual outcomes, of all-cause mortality, initiation of RRT and eGFR based on SCr at day 30 (Visit 9)/day 90 (Visit 10) equal to or less than 75% of the baseline value) and primary, secondary and exploratory endpoint of AKI proportion is evaluated by a contingency table. The following endpoints of AKI proportion will be used;
  - AKI-SCr72h (primary endpoint) and each stage,
  - AKI-SCr7d (secondary endpoint) and each stage,
  - AKI-SCr stage 2 or 3 (within 72 hours after T0), and
  - AKI-SCr stage 2 or 3 (within 7 days after T0)

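### Nephrotoxic-drug and radiocontrast risk factors are sourced only from medication taken before screening, so exposure confined to the interval from screening to surgery is scored No

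*Protocol*

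**What the plan says.** - Protocol 5.2.2, Table 4, lists nephrotoxic drugs and radiocontrast agents as AKI risk factors and gives the source of each as "Recorded in previous medication". The table title adds "Data Source for Capture at Screening or Visit 2".
- Protocol 5.1.3 splits medication at screening: "use of previous (up to 28 days before screening) and concomitant (any medication between screening and surgery". Its Medication Treatment paragraph sets the look-back: "Previous medicines taken within the 28 days prior to screening (visit 1) will be recorded".
- The same paragraph states that, to assess what nephrotoxic drugs contribute to AKI after surgery, "all medications taken from screening to day of surgery should be recorded". It singles out intravenous radio-contrast and aminoglycosides.
- SAP 6.5 keeps the split: "Previous medication is defined as medication with at least one dose taken before the date of the screening". Concomitant medication needs at least one dose on or after the screening date.
- SAP Tables 8 and 13 carry nephrotoxic drugs and "Radiocontrast Agents" as Yes/No items without a derivation. SAP 7.9.1 computes an unadjusted risk ratio, true positive rate and true negative rate for each Table 13 factor.
- A separate item, use of intravenous radio-contrast, is derived in SAP Table 6, footnote 3, from concomitant records only, for "use of Intravenous Radio-contrast between the date of screening and T0 of the date of surgery". It feeds the Table 12 subgroup and its own row in Table 13.

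**The concern.** The protocol names one interval as the reason for recording nephrotoxic medication, namely screening to surgery. It then sources the two risk factors from the interval that stops where that one starts. A contrast injection or a short aminoglycoside course begun after Visit 1 and before surgery is concomitant medication, so a programmer who follows Table 4 and SAP 6.5 scores it No.

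At stake is one exploratory objective: finding subject characteristics that identify patients at risk of AKI, for which up to 440 observational subjects are followed. Nephrotoxic drugs and contrast are among the candidate factors. If truly exposed subjects sit in the No group, both factors look less predictive than they are.

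**Working it through.** The plan states no figure on this point, so there is none to reproduce. The check traces the definitions and then illustrates the size.

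**1. Which exposures are lost**

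| Exposure before surgery | Previous (SAP 6.5) | Concomitant (SAP 6.5) | Table 4 flag |
|---|---|---|---|
| Only before screening | yes | no | Yes |
| Started before screening and continued | yes | yes | Yes |
| Only from screening to surgery | no | yes | **No** |

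Only the last row is mis-scored. It consists mainly of one-off contrast and short courses started after screening.

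**2. How much of a fixed look-back the flag sees**

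Visit 1 may be up to 28 days before surgery (protocol 2.2.1) or within 2 days of it (Table 1, footnote 17). Let it be d days before surgery. Of the 28 days before T0, previous medication covers (28 − d)/28:

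- d = 2: 26/28 = 93%
- d = 14: 14/28 = 50%
- d = 20: 8/28 = 29%
- d = 28: 0%

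The previous and concomitant records together start d + 28 days before surgery. They therefore cover any look-back of up to 28 days in full for every subject.

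**3. Effect on the risk ratio (exposed versus unexposed)**

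The documents give no exposure rates, so these inputs are assumptions: true risk ratio RR = 1.5; share E exposed; share s of the exposed scored Yes; no unexposed subject scored Yes; missed exposure unrelated to outcome. The Yes group is then purely exposed and the No group is mixed:

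observed RR = RR ÷ {[E(1 − s)·RR + (1 − E)] / [E(1 − s) + (1 − E)]}

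Take s = 0.29, which is the coverage at d = 20 for a single dose falling uniformly over 28 days:

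- E = 0.2: E(1 − s) = 0.142. The No-group factor is (0.213 + 0.8)/(0.142 + 0.8) = 1.075. Observed RR = 1.5/1.075 = 1.39, about 1.4.
- E = 0.5: E(1 − s) = 0.355. The factor is (0.5325 + 0.5)/(0.355 + 0.5) = 1.208. Observed RR = 1.5/1.208 = 1.24.

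The range over other assumptions:

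| E | s = 0.75 | s = 0.50 | s = 0.25 |
|---|---|---|---|
| 0.2 | 1.46 | 1.42 | 1.39 |
| 0.5 | 1.36 | 1.29 | 1.24 |
| 0.8 | 1.20 | 1.13 | 1.09 |

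**4. Effect on the true positive and true negative rates**

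The SAP does not define these. I take them as the share of AKI subjects scored Yes and the share of AKI-free subjects scored No. Under the same assumptions the true positive rate is multiplied by s, whatever RR and E are:

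- E = 0.2: true value 0.30/(0.30 + 0.80) = 0.27; observed 0.29 × 0.273 = 0.08.
- E = 0.5: true value 0.75/(0.75 + 0.50) = 0.60; observed 0.29 × 0.60 = 0.17.

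The true negative rate rises. With an assumed AKI risk of 0.30 in the unexposed (0.45 in the exposed):

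- E = 0.2: from 0.56/(0.56 + 0.11) = 0.84 to (0.56 + 0.71 × 0.11)/0.67 = 0.95.
- E = 0.5: from 0.35/(0.35 + 0.275) = 0.56 to (0.35 + 0.71 × 0.275)/0.625 = 0.87.

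**The case against.** **The Table 4 title.** It refers to capture at screening or Visit 2, and Visit 2 baseline includes medication use between screening and surgery. On that reading, previous simply means before surgery, and Table 4 agrees with 5.1.3. SAP Tables 8 and 13 cite neither Table 4 nor the 6.5 definition, and the table specifications are not among the documents. This reading is possible, so the No is inferred rather than stated. But the only written definitions of previous medication, in protocol 5.1.3 and SAP 6.5, both stop at screening. Table 13 also sits better with the narrow reading, because it has a separate contrast row limited to screening to T0. If the broad reading was meant, the SAP needs to say so.

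**Overlap.** Drugs continued across screening count on both sides and are scored correctly. This stands, and it limits the problem to exposure confined to the later interval. For contrast, the second Table 13 row picks up that interval, although neither row alone measures presurgery exposure. Nephrotoxic drugs have no second row.

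**The radio-contrast subgroup.** A reader might infer that the Table 12 subgroup is wrong too, because it ignores contrast given before Visit 1, and that its treatment effects are diluted. The documents do not support calling that an error. Protocol 7.4.3 prespecifies screening to surgery, the SAP implements it, and the window matches the purpose stated in 5.1.3. The arithmetic above concerns exposed against unexposed subjects, not treatment ratios within subgroup levels. Subgroup membership is settled before randomization, so misclassification does not by itself pull each treatment ratio towards 1.

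**Conclusion.** The point holds for the two risk factors in protocol Table 4 and SAP Tables 8 and 13. As written, exposure confined to screening-to-surgery is scored No, although that is the interval 5.1.3 singles out.

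The consequence is limited to the baseline risk-factor table and the exploratory prognostic analysis. How large it is there cannot be fixed from the documents. With a true risk ratio of 1.5, the illustration gives 1.39 to 1.24 at 29% detection for 20% to 50% exposed, and 1.46 to 1.09 over the wider range. It rests on non-differential error, no false Yes and assumed exposure shares.

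A reader might also infer a threat to the main efficacy result. There is none: the primary and secondary tests do not use these factors, and the sample size does not depend on them.

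**What to change.** In protocol Table 4 and SAP Tables 8 and 13, derive nephrotoxic drugs and radiocontrast agents from the previous and concomitant medication records together. Score Yes for any dose before T0 within one look-back that is the same for all subjects. Any length up to 28 days before T0 is fully covered; the sponsor should fix it before unblinding. The SAP should state this derivation explicitly, including which drugs count as nephrotoxic.

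The radio-contrast subgroup in SAP Table 12 can stay as prespecified. Its cut at Visit 1 falls anywhere from 1–2 to 28 days before surgery, depending on the subject, so the combined flag can be reported beside it as a sensitivity version.

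The cost is derivation wording and programming. Both records are already collected, and no visit or procedure changes.
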